4.4 Inclusion and Exclusion Criteria

Inclusion criteria:

Phase 1: 18 years old and older, English and/or Spanish speaking, living in the US, PHQ-9 score ≥ 10 , and received a diagnosis of depression from a Talkspace intake clinician.

Phase 2: 18 years old and older, English and/or Spanish speaking, living in the US in a state where a participating licensed Talkspace clinician is available, PHQ-9 score ≥ 10 .

- Prolific recruitment survey: Prolific users who are 18 years old and older, English speaking, living in the US in a state where a participating licensed Talkspace clinician is available.

Unavailable therapist: Potential participants who are eligible at an initial baseline but unable to enroll in the study due to lack of therapist availability will be contacted by Talkspace via email to let them know. In that email, they will be offered immediate care at Talkspace and will be told that they will be contacted when a study therapist is available, unless they opt out of further communication. Once a study therapist is available in their state, any waiting potential participants will either be randomized or, if it has been more than 30 days since their initial eligibility baseline, will be sent a link to complete a new baseline. All eligibility criteria should still be met at the new baseline in order for the participant to be randomized. However, participants with PHQ-9 scores between 5 and 10 may be randomized if they remain interested in participating in the study. No one with a PHQ-9 score < 5 will be randomized. The study team will remove recruitment materials from states with no therapist capacity, so these situations should be limited to individuals that enter the enrollment pipeline while space is available but do not complete the enrollment activities prior to a therapist's caseload filling.

Exclusion criteria:

Phase 1: Under 18 years of age, does not speak English or Spanish, and does not meet criteria for a depressive disorder. Individuals with active suicidal ideation or with a primary diagnosis of psychosis will be excluded and referred to appropriate care.

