5.1 Procedures

Phase 2: During the baseline assessment, participants will respond qualitatively to the following question: "How would you describe the top issue you would like help with in therapy? Describe the problem as something that is potentially changeable in therapy. So rather than writing 'Going through a divorce' you might write 'Feeling sadness and anger while I'm going through a divorce.'" Upon participant completion of this field, REDCap will send an automated alert to the UW study team that information has been entered in this field. A clinical member of the UW study team will review this information within 1 business day. If actionable information (e.g., risk of harm to self or others) is shared in that field, the UW study team will alert the Talkspace study team, and the participant will not be enrolled in the study. Because this information is provided prior to randomization and thus prior to assignment to a clinician, the Talkspace study team will connect the individual to a clinician to complete a full assessment and escalate through Talkspace's established crisis procedures.

Identification and Management of Suspected Fraudulent Participation: Consented participants who have not yet started treatment and are identified post-consent to meet fraudulent criteria will be contacted via email notifying them of their removal from the study. In the consent form, participants are informed that they may contact the study team to receive a detailed explanation as to why their data did not reach study standards. Participants who have started treatment in the study and are later identified to meet fraudulent criteria will be contacted via email notifying them of their removal of treatment and from the study. In the consent form, participants are informed that they may contact the study team to receive a detailed explanation as to why their data did not reach study standards. The participant's assigned therapist will also be notified via email about the participant's removal from the study.

Randomization:

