Phase 1: See Section 3.0. Randomization will be determined using www.randi2.org, an open-source web-based RCT randomizer that supports many types of algorithms (complete, biased coin, truncated randomization, block randomization, and the Wei's urn model randomization). Participants will be randomized to the first level of care using Wei's urn randomization blocking by recruitment, which adapts the probability of randomization to condition by the balance in the group assignments. This tightly controls balance while permitting randomization. Level 1 participants who respond to treatment will continue in their baseline condition. Level 1 participants who do not respond to treatment by week 5 (PHQ-9 score > 50% of baseline PHQ-9 score, or CGI-I score >2) will be re-randomized to receive MBP and supplemental weekly or monthly VBP.

Phase 2: See Section 3.0. Baseline Level 1 randomization to MBP or VBP occurred on REDCap and will be triggered by a research coordinator upon enrollment. We will use simple randomization with pre-specified and concealed blocks by therapist. Level 2 randomization will occur on REDCap. Level 1 participants who respond to treatment will continue in their baseline condition. Level 1 participants who do not respond to treatment by week 5 (PHQ-9 score > 50% of baseline PHQ-9 score, or CGI-I score >2) will be re-randomized to receive MBP and supplemental weekly or monthly VBP.

Treatment Procedures: All procedures described here are methods developed and used by Talkspace, unless otherwise specified. There are four interventions in this study: Level 1 interventions are unlimited MBP and weekly VBP. Level 2 interventions are MBP with monthly VBP, and MBP with weekly VBP. After participants give consent to participate, they will be randomized to one of the two Level 1 conditions. As per Talkspace's model, participants are offered a choice of three therapists, based on the state the therapist is licensed in. Procedures for consumer/clinician initiation are the same for each treatment option. Participants can contact their therapists any time after they are provided with choices. Once participants reach out to a therapist, therapists connect within 15 minutes to 24 hours, depending on the time of day the participants made their choice and the therapists' office

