Level 1 Power: For the quantitative primary outcome (PHQ-9) we have greater than 80% power to detect a 0.20 standard deviation across groups which corresponds to a clinically meaningful small difference. For a binary success indicator, we will consider a 50% reduction in PHQ-9 from baseline to week 5, and we have greater than 80% power to detect an absolute difference of 10% (e.g., 60% of subjects with >50% improvement versus 70% of subjects with >50% improvement).

Level 2 Power: The primary comparison in the second stage is the comparison of the Ultimate Plan (UP; MBP with weekly VBP) versus the Premium Plan (PP; MBP with monthly VBP) for each of the first stage randomization groups (MBP and VBP). We expect a second stage analysis sample of 324 subjects, and this corresponds to 80% power to detect a 0.32 standard deviation difference across the UP and PP groups when pooling across the primary MBP and VBP strata. Our primary second stage analysis will construct an overall UP versus PP difference stratifying on first stage randomization, and secondary analysis will consider the UP versus PP difference within the MBP and VBP groups separately.

Accounting for Provider Effects: Each provider will treat both MBP and VBP patients. Therefore, our primary analyses will all cluster on provider either using linear mixed models or generalized estimating equations to yield valid statistical inference. However, since treatment condition will vary within provider, the impact of provider clustering is to effectively balance or control for provider effects. Therefore, our power calculations are conservative since they do not account for the potential increase in precision associated with control for provider effects. Such within-provider randomization is in contrast to traditional cluster randomized trials where providers treat all patients in one study condition and thus increase variability associated with treatment comparisons through the well-known intra-cluster correlation coefficient.

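### Response (1c) and remission (1d) are tested by chi-square with no therapist term, although Phase 2 Level 1 allocation is blocked by therapist

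*Combined protocol and SAP*

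**What the plan says.** **Allocation.** Section 5.1, Randomization (Phase 2): "We will use simple randomization with pre-specified and concealed blocks by therapist". A research coordinator triggers the draw in REDCap at enrolment. No block size is given.

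**Therapist and draw.** Section 5.1 says of the free-text baseline item: "Because this information is provided prior to randomization and thus prior to assignment to a clinician". Under Treatment Procedures it says "After participants give consent to participate, they will be randomized to one of the two Level 1 conditions", and then that "participants are offered a choice of three therapists, based on the state the therapist is licensed in". The same paragraph adds: "Procedures for consumer/clinician initiation are the same for each treatment option". The text on suspected fraud says that the participant's "assigned therapist will also be notified via email". Section 4.4 speaks of people who "do not complete the enrollment activities prior to a therapist's caseload filling".

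**Provider rule.** Section 8.0, Accounting for Provider Effects, says that every provider treats patients in both arms, that all primary analyses will cluster on provider through mixed models or GEE, and that the power figures are therefore conservative.

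**Level 1 outcomes.** Section 8.0, Level 1 Power, gives power for the PHQ-9, which it calls the quantitative primary outcome, and for response: "For a binary success indicator, we will consider a 50% reduction in PHQ-9 from baseline to week 5".

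**Tests.** Section 8.0, Statistical Analyses, and Table 2 assign a three-level mixed model with a clinician level to 1a and 1b, and chi-square tests to 1c and 1d. The two-level logistic model has Level 2 condition as its predictor, so it does not cover the MBP versus VBP contrast of 1c and 1d.

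**The concern.** When allocation is blocked within therapist, the analysis should use therapist too. A test that leaves it out keeps between-therapist variation in its standard error, although the design has removed that variation from the arm contrast. The continuous Level 1 outcomes are modelled with a clinician level and the binary ones are not, so two parts of the same hypothesis family treat therapist differently. If 1c is read as one of the primary analyses, this also departs from the SAP's provider rule. What is at stake is a small loss of precision for response and remission, and consistency between design and analysis.

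A second matter is one of wording. Simple randomization and blocked randomization are different schemes, and no section states how a therapist's block is identified when the coordinator triggers the draw.

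**Working it through.** **Inputs from section 8.0:** 1,000 evaluated participants; 60% versus 70% response; 0.20 SD on the PHQ-9.

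**Assumed, because not stated:** 1:1 allocation (500 per arm); two-sided 5% level; intraclass correlation (ICC) 0.02, 0.05 or 0.10; 20 to 40 patients per therapist (m); single-timepoint approximation.

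**Step 1. Reproduce the stated power.**
- Response: pooled SE = √(2 × 0.65 × 0.35/500) = 0.03017; unpooled SE = √(0.24/500 + 0.21/500) = 0.0300. Power = Φ[(0.10 − 1.96 × 0.03017)/0.0300] = Φ(1.36) = 91.3%.
- PHQ-9: Φ(0.20 × √1000/2 − 1.96) = Φ(1.20) = 88.5%.

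Both agree with the stated figure of more than 80%.

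**Step 2. Chi-square when the blocks work.** Let v be the variance across therapists of the share of their patients in MBP. For a test that ignores therapist, the ratio of true to assumed variance is DEFF = 1 − ICC + ICC × m × v/0.25. Working blocks give v = 0, so DEFF = 1 − ICC.
- Type I error = 2 × [1 − Φ(1.96/√DEFF)].
- Chi-square power = Φ[(0.10 − 1.96 × 0.03017)/(0.0300 × √DEFF)].
- Therapist-adjusted power = Φ[0.10/(0.0300 × √DEFF) − 1.96].

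| ICC | DEFF | Type I error, chi-square | Power, chi-square | Power, adjusted | Points lost |
|---|---|---|---|---|---|
| 0.02 | 0.98 | 4.8% | 91.6% | 92.0% | 0.5 |
| 0.05 | 0.95 | 4.4% | 91.9% | 92.8% | 0.9 |
| 0.10 | 0.90 | 3.9% | 92.5% | 94.0% | 1.5 |

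The last column is taken before rounding. With the pooled SE in the adjusted test as well, the loss is 0.3, 0.7 and 1.4 points.

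A simulation (20,000 runs per cell, 60% in both arms) gave chi-square type I error of 4.8%, 4.2–4.5% and 3.8%. A therapist-stratified Mantel-Haenszel test, standing in for the logistic model, gave 4.8–5.1%.

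**Step 3. Therapist chosen after the draw, independently of arm.** Then v = 0.25/m by chance and DEFF = 1 − ICC + ICC = 1. The chi-square test has its nominal 5% error.

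**Step 4. How uneven would therapists have to be to affect the power statement?** For a random-intercept model of the PHQ-9, effective N = 4N × [(0.25 − v)/(1 − ICC) + v/(1 − ICC + m × ICC)].
- Setting effective N = N gives v = [1 + (m − 1) × ICC]/(4m), an SD of MBP share of 0.131–0.190 at m = 20 and 0.105–0.175 at m = 40. Chance alone gives 0.5/√m = 0.112 and 0.079. Above the break-even values the word conservative no longer holds.
- Power of 80% needs effective N = [2 × (1.96 + 0.8416)/0.20]² = 785. PHQ-9 power falls below 80% only if the SD exceeds about 0.30 to 0.45.

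**Step 5. Therapist choice dependent on arm.** If therapists with better outcomes are chosen more often in one arm, a random intercept leaves part of the confounding. In the linear analogue, the fraction left is 0.25b/[(0.25 − v)w + vb], with w = 1/(1 − ICC) and b = 1/(1 − ICC + m × ICC). Take an assumed SD of MBP share of 0.15 (v = 0.0225):
- ICC 0.02, m = 20: w = 1.020, b = 0.725, fraction 0.73.
- ICC 0.10, m = 40: w = 1.111, b = 0.204, fraction 0.20.

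**The case against.** The best defence is that the plan breaks no rule of its own. At Level 1 it attaches the word primary only to the PHQ-9, whose analysis does carry a clinician level. Response is called a binary success indicator, and having a power statement does not make it primary. The chi-square tests are an explicit choice, and with working blocks they are valid. This stands in large part: the mismatch with the provider rule depends on how far primary reaches, and for remission, which has no power statement, the link is weaker still. It does not answer the design point, because a test that drops the blocking factor gives up precision that the allocation was set up to provide.

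A reader might infer that therapist blocks were impossible because the therapist was unknown at the draw. The documents do not support that. The sentence placing randomization ahead of clinician assignment ("Because this information is provided prior to randomization and thus prior to assignment to a clinician") fits a single step in which the coordinator fixes the therapist and draws from that therapist's list. Section 4.4 refers to caseloads filling during enrolment, and section 5.1 to an assigned therapist. The choice of three is introduced as the platform's usual model. The word simple may only contrast with the adaptive urn of Phase 1. What is missing is a sentence of detail.

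**Conclusion.** Minor. The 1c and 1d tests should reflect the therapist blocks and do not. If the blocks work, the cost is a type I error of about 4.8% to 3.9% and about 0.5 to 1.5 power points. These figures rest on an ICC and a 1:1 allocation that the documents do not give.

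Three stronger readings are not supported:
- **That the chi-square tests are anti-conservative.** This needs therapists' arm mix to vary beyond chance. Simulations that assumed such variation gave errors of 5.3–8.2% (mild) and 6.0–20.6% (strong, ICC up to 0.20), but the documents give no sign of it, and the statement that initiation is the same for each option points the other way.
- **That the power statement falls without within-therapist balance.** The figure of more than 80% ignores provider and reproduces. Only the description of it as conservative depends on balance.
- **That a therapist-clustered model is right in every case.** If therapist was chosen after the draw and the choice depended on arm, therapist is a post-randomization variable. Conditioning on it changes the estimand, and a random intercept removes only part of the confounding.

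**What to change.** **Analysis.** In section 8.0 and Table 2, test 1c and 1d with the two-level logistic model (clients within clinicians) with Level 1 condition as predictor. Name a GEE or a therapist-stratified test as the fallback if it does not converge. Keep chi-square and Cramér V as descriptive.

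**Wording.** In section 5.1, delete the word simple and state how the therapist is identified at the draw. Report MBP and VBP counts per therapist. The order of procedures need not change.

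**Condition.** If the therapist turns out to have been chosen after the draw and the choice depended on arm, report the unadjusted as-randomized comparison alongside. Make the statements in section 8.0 about conservative power and within-provider randomization conditional on therapist choice being independent of arm.

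**Cost.** Minor extra analysis and a few text edits, with no extra participants. The odds ratio becomes conditional on therapist, and the model may converge poorly where caseloads are very small.

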hours. All therapists maintain office hours, typically 9-6 in their time zone, 5 days a week (typical to private practice models of care). Talkspace patients are offered an opportunity to participate in a complementary, but not compulsory, live video session with their chosen therapist. Therapists are required to offer it, but historically, only 24% of patients avail themselves of this service. Although patients can use Talkspace services for as long as they and the therapist feel it is necessary, on average, patients use 10 weeks of care, and for the purposes of this study, participants will be told they have 12 weeks of care available to them.

Assessment Procedures: For both study phases, participants will continue to complete Talkspace's standard assessments (PHQ-9 and Generalized Anxiety Disorder-7 [GAD-7]¹⁰), which are delivered every 3 weeks. For the 12 weeks that the participant is in the study, these assessments will be shared with the study team.

All assessments discussed in the following section will be completed using REDCap. Participants will receive links to complete the assessments via text message using Twilio, a REDCap extension that allows for SMS communication with participants. Participants will complete a baseline assessment, 2 follow-up assessments (6- and 12-weeks), daily ratings, and weekly assessments. Participants are given a 3-day window to complete a brief assessment of mood and improvement (weekly assessment) and a follow-up assessment of mood, functioning, cognition, improvement and satisfaction. If a participant does not complete the weekly or follow-up assessment within 24 hours, the participant will receive a reminder SMS message. If participants do not complete the assessment within 24 hours of the reminder, an email reminder is sent. REDCap provides the project coordinator with daily information about research participants' completion of assessments. These data will be used to assess the utility of the study reminder system in study retention and user engagement with the research protocols.

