Communication: Participants will receive check-in emails throughout the study reminding them of the study timeline and upcoming study assessments, other elements to anticipate, or checking in on disengaged participants to inquire about their participation status. All communication regarding treatment will be handled by Talkspace therapists within the Talkspace platform. Participants will be directed to raise any study-related questions with their therapist and/or by responding to emails from the study team or contacting the study team via phone or email.

Withdrawal of Participants: A participant may be withdrawn from the study if it is determined that they are in need of a higher level of psychiatric care than what can be provided by the study. In that case, the participant would not complete any additional study procedures. Appropriate referral and treatment would be the responsibility of the Talkspace therapist. When a participant is withdrawn from the study without their consent, the Talkspace research coordinator will directly follow up with the participant and their therapist in separate emails within 24 hours of this determination, and a copy of these communications will be sent to the UW study team for record keeping. UW coordinators will record these events in REDCap, turn off automatic surveys, and post any incentives pending delivery for the participant to be sent in the next payment cycle.

If participants choose to cease care prior to completing 12 weeks of treatment, the participant will continue to receive notifications from REDCap to complete assessments. If a participant does not complete a weekly assessment in REDCap in the first 24 hours, they will receive an automated reminder via SMS, and if in the following 24 hours they do not complete the weekly assessment, they will receive an automated reminder via email. SMS notifications for each daily survey and weekly assessment will continue to be sent throughout the 12 weeks to give participants the opportunity to complete them even if they are not responsive. If a participant reaches out to the study team via email to withdraw from the study fully, the participant will be disenrolled and no longer sent notifications via SMS and email. In addition to text and video chat services, Talkspace maintains a virtual bookshelf of articles, worksheets and educational videos therapists can share with patients.

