Statistical Analyses: See Table 2 for analyses by hypothesis. Treatment disengagement, treatment response, and remission will be analyzed using chi-square tests and Cramér V effect sizes. 2-level linear mixed effects models using full information maximum likelihood (FIML) and an unstructured covariance matrix with client nested within clinician will be used for analyses at a single timepoint. Models predicting binary outcomes at a single timepoint will be evaluated using 2-level logistic regression models with Cholesky factorization with client nested within clinician, with Level 2 condition as the independent variable. Effect sizes for these models will be computed via pooled standard deviations of conditions at that timepoint.

Models assessing changes across time will be evaluated using 3-level mixed effects regression models with timepoint nested within client nested within clinician using FIML and an unstructured covariance matrix. Client-level effects will be allowed to randomly vary, and clinician will be a clustering variable with condition approximately balanced within clinicians. Analyses with time from baseline to week 12 will include a spline variable to account for differences in outcome trajectories from baseline to week 5 and from week 6 to week 12.

The mixed-effects models will utilize all available data. Prior research has demonstrated equivalence of longitudinal mixed model analyses using imputed versus non-imputed data (e.g., between multiple imputation and FIML).¹³ Theoretically, there is no reason to expect substantial differences between FIML and MI with a reasonable sample size and complete predictors.¹⁴ Thus, missing data will not be imputed. Cohen's *d* clinical outcome effect sizes for the model predicting PHQ-9 scores by Level 2 condition from weeks 6 to 12 will be computed as the difference between model-estimated means divided by the pooled standard deviations when the second condition

was assigned at week 6. All remaining clinical outcome effect sizes will be computed as the difference between model-estimated means divided by the pooled baseline standard deviations.

We will use the Benjamini-Hochberg procedure to account for Type 1 error by adjusting for familywise error within hypothesis families (e.g., within Hypotheses 1a to 1d; within Hypothesis 2). *P* values and effect sizes with 95% confidence intervals will be reported, as appropriate.¹⁵

Table 2. Analyses by Hypothesis

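### Participants withdrawn for needing a higher level of care lose outcome follow-up, and the SAP does not say how they count in the week-12 response and remission tests

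*Combined protocol and SAP*

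**What the plan says.** The combined protocol and SAP, section 5.1 (Withdrawal of Participants), treats two kinds of early leaver differently.

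- **Withdrawn by the study.** "A participant may be withdrawn from the study if it is determined that they are in need of a higher level of psychiatric care" than the study can offer. "In that case, the participant would not complete any additional study procedures", and "UW coordinators will record these events in REDCap, turn off automatic surveys". The participant need not have asked for this.
- **Stops care by choice.** Here "the participant will continue to receive notifications from REDCap to complete assessments", and these continue for the full 12 weeks. Under this paragraph, such a person loses the surveys only by asking to leave the study altogether.

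The Talkspace platform collects its own PHQ-9 every three weeks, but section 5.1 limits the sharing: "For the 12 weeks that the participant is in the study, these assessments will be shared with the study team". That does not clearly cover anyone already withdrawn.

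In section 8.0 (Statistical Analyses), "Treatment disengagement, treatment response, and remission will be analyzed using chi-square tests". For the longitudinal outcomes, "The mixed-effects models will utilize all available data", fitted by full information maximum likelihood (FIML), and the argument about missing data ends "Thus, missing data will not be imputed". Table 2 takes early response and remission from weeks 3 to 5 and late response and remission from week 12. Neither the text nor Table 2 says how a participant with no week-12 score is classified. No sensitivity analysis for missing data is given.

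**The concern.** Outcome collection stops by protocol for a reason related to the outcome. A person judged to need more psychiatric care than the study provides is unlikely to be a responder or remitter at week 12, yet that is the person whose week-12 PHQ-9 is no longer sought.

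If the chi-square tests use only observed scores, two things follow. Response and remission rates are overstated wherever such withdrawals occur. If withdrawals are commoner in one arm, that arm is flattered, because more of its failures have left the denominator.

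The Hypothesis 2 response test is the most exposed. It compares weekly with monthly video among people who have already not responded, and its cells are small.

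**Working it through.** **The plan's own figure.** Section 8.0 enrols 1,250 to evaluate 1,000 with 20% dropout: 1,000 / (1 − 0.20) = 1,250, which reproduces. The 20% is not split by reason, so the share withdrawn for a higher level of care is unknown. The rates below are assumptions.

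**Response test, as hidden difference.** Let w be the share withdrawn. Assume 60% response among those not withdrawn in both arms and none among those withdrawn. An observed-case test sees 60% in each arm. The rate among everyone randomized is (1 − w) × 0.60.

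| Withdrawn, arm A vs arm B | Rate in A | Rate in B | Difference hidden |
|---|---|---|---|
| 2% vs 5% | 0.98 × 0.60 = 58.8% | 0.95 × 0.60 = 57.0% | 1.8 points |
| 2% vs 8% | 58.8% | 0.92 × 0.60 = 55.2% | 3.6 points |
| 5% vs 5% | 57.0% | 57.0% | 0; both overstated by 3.0 points |

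**The same problem, as false difference.** Suppose instead that the true rate is 60% in both arms. The observed rate is then 0.60 / (1 − w).

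- 2% vs 5%: 0.60/0.98 = 61.2% against 0.60/0.95 = 63.2%, a false difference of 1.9 points before rounding.
- 2% vs 8%: 61.2% against 0.60/0.92 = 65.2%, a false difference of 4.0 points.

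Take 500 per arm before withdrawal (1,000 evaluated; 1:1 allocation and two-sided 5% level assumed). The standard error is the square root of p₁(1 − p₁)/n₁ + p₂(1 − p₂)/n₂, about 0.031 in both cases. The chance of a false positive is then about 9.5% and 24.8% in place of 5%.

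**Hypothesis 2 cells.** The expected Level 2 sample is 324. Table 2 contrasts weekly with monthly video within each Level 1 arm, which makes four cells. With an equal split (assumed), 324 / 4 = 81 per cell, so five withdrawals are 5/81 = 6.2% of a cell.

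**Mixed models.** Weekly scores before withdrawal stay in the model, so only worsening that they do not predict causes bias. The bias in the PHQ-9 contrast is approximately (difference in withdrawn share) × (unpredicted worsening in SD).

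- Low end: 0.01 × 0.5 = 0.005 SD, which is 2.5% of the 0.20 SD in the Level 1 power statement.
- Middle: 0.03 × 1.0 = 0.03 SD, or 15%.
- High end: 0.06 × 1.5 = 0.09 SD, or 45%.

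**The case against.** Much can be said on the other side, and a good part of it stands.

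- **Exclusion from the denominators is not written down.** The no-imputation sentence closes an argument about FIML and mixed models. It does not rule out counting these people as non-responders. This stands: the defect is an unspecified rule, and observed-case analysis is only its natural reading.
- **The mixed models do not simply place withdrawn people on the path of those who stayed.** Each person's earlier weekly PHQ-9 scores and the client-level random effects inform the fit. This stands, and confines the problem there to unpredicted worsening.
- **Week 5 has a cushion.** Someone withdrawn after a week-3 or week-4 score can still be classified in the week 3 to 5 window. Week 12 has no such fallback.
- **A reader might infer that the worst outcomes are removed by design.** The documents do not say that. The trigger is discretionary and could concern a problem other than depression. A poor PHQ-9 outcome is a reasonable inference, not a stated fact.
- **A reader might also infer that one modality will trigger more withdrawals.** The documents do not show it. Each provider treats both arms, and the weekly PHQ-9 and its alerts run alike in both. Section 1.1 says that message-based therapists can step in quickly. Contact does differ between weekly video, monthly video and messaging, so unequal withdrawal is possible but undemonstrated.
- **Numbers may be small.** Section 4.4 excludes active suicidal or homicidal ideation, bipolar disorder and psychosis from Phase 2. Section 6.0 manages suicidal ideation by risk assessment and safety planning without naming withdrawal as a step. An 8% rate would use 0.08/0.20 = 40% of that arm's dropout allowance.

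None of this supplies the missing rule or explains why the two kinds of leaver are followed differently.

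**Conclusion.** The concern holds in a limited form. Section 5.1 creates missingness tied to likely poor outcome, and section 8.0 neither says how it is handled nor tests sensitivity to it. The exposure is mainly in the week-12 parts of 1c and 1d and in the Hypothesis 2 response test.

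The hidden differences of 1.8 and 3.6 points rest on assumed withdrawal rates, 60% response among those not withdrawn, no response among those withdrawn, and observed-case testing. With equal withdrawal and equal response there is no between-arm bias, only overstated rates. It would go too far to say that the plan loses about a third of its design difference: the 10-point difference in the power statement is for response at week 5, while the main exposure is at week 12.

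**What to change.** Leave the decision to withdraw as it is. Change the analysis, and the follow-up where feasible.

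1. **Classification.** State in section 8.0 that a participant recorded in REDCap as withdrawn for a higher level of care counts as a non-responder and non-remitter at timepoints after withdrawal in 1c and 1d, and in the Hypothesis 2 response test if withdrawn after Level 2 randomization. Say also whether a score obtained in the week 3 to 5 window before withdrawal stands. Counting withdrawal as failure is one defensible choice among several; what matters is fixing the rule in advance.
2. **Reporting.** Give the number and timing of these withdrawals by Level 1 arm and Level 2 condition.
3. **Sensitivity.** Add a missing-not-at-random analysis of the PHQ-9 models, for example worsening the unobserved scores of these participants by a range of fixed amounts.
4. **Follow-up, where feasible.** Separate withdrawal from study treatment from withdrawal from assessment, and keep offering the PHQ-9 link with opt-out. Later scores would inform the mixed models and item 3. The sponsor must first confirm how the suicidal-ideation alert in section 6.0 is covered for people who have left Talkspace care, since it is passed to a Talkspace therapist who may no longer be treating them.

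Items 1 to 3 need no new data, because section 5.1 already records these events. They cost SAP wording, a little more analysis and slightly lower reported response rates. Item 4 costs a survey setting, a consent sentence and the alert-coverage check. Some people will decline the surveys.
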